#### 4.4 Risks of Harm

There is a risk of discomfort associated with nicotine withdrawal for patients who are quitting smoking. The nicotine patch (an FDA-approved medication) is well tolerated; however there are potential side effects that may arise when using the patch. Each patient will discuss these side effects with their therapist. If questions arise as a result of the patch,

one of the study co-investigators is an Addiction Psychiatrist who will be available to provide patients with information regarding their side effects.

There is a risk that participants' confidentiality could be violated. To reduce the risk of violating confidentiality, several steps will be taken. Only IRB approved members of the research team will have access to the data. The research staff collecting the data will bring the data to the PI within 24 hours of it being collected. Data will only be accessed when coded, entered, or audited. The PI will maintain responsibility for safe data storage. All data will be stored in locked cabinets within locked rooms. Based on these procedures, we anticipate that the risk to confidentiality is very low.

### **HANDLING OF UNEXPECTED OR ADVERSE EVENTS**

#### ***Response to new or unexpected findings and to changes in the study environment:***

The study team will meet on a quarterly basis while participants are in the study. The team will monitor the study according to the guidelines specified in the study protocol and the operating procedures established at the initial meeting, unless the team determines during the course of the trial that modification of the guidelines is in the best interest of the study and its participants. Such a decision may be based on new information that emerges during the course of the study (e.g., publication of the results of a similar trial), realization of inappropriate initial study assumptions, or the occurrence of an unanticipated scenario.

#### ***Identifying, managing, and reporting adverse events:***

There is a risk of discomfort associated with nicotine withdrawal for patients who are quitting smoking. The nicotine patch (an FDA-approved medication) is well tolerated; however there are potential side effects that may arise when using the patch. Each patient will discuss these side effects with their therapist. If questions arise as a result of the patch, one of the study co-investigators is an Addiction Psychiatrist who will be available to provide patients with information regarding their side effects.

The research staff member who observes or is notified of a possible adverse event will notify the Principal Investigator within 24-hours. Events which are 1) Unexpected in terms of nature, severity or frequency, given the research protocol, IRB-approved informed consent document, product labeling and other sources of information, and given the characteristics of the subject population being studied, 2) Related or possibly related to participation in the research, and 3) Potentially place the research subjects or others at a greater risk of harm (including physical, psychological, economic or social harm) than was previously known or recognized will be reported to the IRB in a written Unanticipated Problems/Adverse Events In Human Subjects Research Report. If these events are deemed "serious," we will report within one week of discovery. If not, we will report within two weeks of discovery. In addition, if a death occurs within 30 days of the intervention, whether or not it was deemed study related, we will report within 24-hours of discovery.

Any item listed on the Adverse Events Log that is deemed to be of more than mild severity will be discussed with the Addiction Psychiatrist within 7 days of the study appointment at which the research staff learned of it. The Addiction Psychiatrist will document this "Moderate" or "Severe" AE and the recommended action, if any, in signed progress notes.

The Principal Investigator will meet with research staff to discuss the impact of participation upon patients. If concerns are reported, the Principal Investigator will discuss modification of the research procedures with the research team, and request IRB approval of proposed

changes (if any). We believe that this level of monitoring is commensurate with the degree of risk to participants.

Adverse events will be reviewed weekly at research meetings, followed by completion of a separate progress note inserted into the participant's binder. Each adverse event will now have a space to indicate the date a progress note was made. The AE list and related progress notes will be on a different color paper than the rest of the chart to ensure that proper attention is paid.

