#### **4. Study Variables**

##### ***4.1 Independent Variables or Interventions***

We will provide 8-weeks of free counseling to participants. Study therapists will utilize the “Persistence-Targeted Smoking Cessation-Schizophrenia (PTSC-S)” manual developed by [name], which is based on cognitive behavioral therapy. PTSC-S is an 8-session, individual, smoking cessation counseling strategy that focuses heavily on using cognitive behavioral therapy targeted at disputing automatic thoughts that may reduce task persistence for smokers with schizophrenia. While disputing automatic thoughts will be the focus of each session, skill building and support will also be included. Participants will be asked to complete homework assignments between sessions – including keeping a daily thought record to monitor automatic thoughts that may put them at risk for smoking. A daily thought record is a commonly used cognitive behavioral therapy homework assignment in which participants practice identifying and evaluating their thoughts. Participants will also track their daily cigarette use and nicotine patch use for homework. Participants will use commonly used, established measures to provide brief assessment information at the end of each session (i.e., nicotine dependence, tobacco use, nicotine lozenge use, nicotine craving, and nicotine withdrawal).

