###### ***4.1.1 Drug or Device Interventions***

We will give participants a 10-week supply of the nicotine transdermal patch (an FDA-approved, over-the-counter medication) to be used starting on their Quit Date. Although the nicotine patch is commercially available without a doctor’s prescription, Co-I [name] (an addiction psychiatrist) will provide medical monitoring during this study. Consistent with the product insert, participants will be instructed to use one nicotine patch daily, and to apply it upon awakening at about the same time each day. Subjects will be instructed to vary the site of application of the patch daily to minimize any skin irritation. They will use the 21mg patch for the first 8-weeks, then 2-weeks of the 14mg patch.

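### A Severe adverse event may wait up to 7 days for required discussion with the medical monitor, as a Moderate one may, and that discussion has no stated deadline if staff learn of the event outside a study appointment

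*Combined protocol and SAP*

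**What the plan says.** Section 4.1.1 states that a co-investigator, an addiction psychiatrist, "will provide medical monitoring during this study". The same section sets the exposure: "We will give participants a 10-week supply of the nicotine transdermal patch", starting on the Quit Date, and "participants will be instructed to use one nicotine patch daily". Section 4.1 says: "We will provide 8-weeks of free counseling to participants".

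The section on identifying, managing and reporting adverse events gives the only deadline for the psychiatrist's input on an event. An item on the Adverse Events Log "deemed to be of more than mild severity will be discussed with the Addiction Psychiatrist within 7 days of the study appointment" at which staff came to know of it. The next sentence covers both grades together: the psychiatrist documents a Moderate or Severe "AE and the recommended action, if any, in signed progress notes". No other section sets a shorter limit for Severe.

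Notice to the Principal Investigator is faster and does not depend on a visit: "The research staff member who observes or is notified of a possible adverse event will notify the Principal Investigator within 24-hours".

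**The concern.** The plan wants the medical monitor's recommendation on every event above mild. For a drug applied daily, that recommendation is worth most when it comes early. Two features of the wording work against this.

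- The limit does not shorten as severity rises. A Severe event may wait as long as a Moderate one.
- The clock is tied to an appointment. When staff learn of an event by telephone or other unscheduled contact, the duty to discuss it remains but no date is attached.

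At stake is whether patch use in a participant with a severe event gets timely medical review. No hypothesis, endpoint or analysis depends on it.

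**Working it through.** This is mainly a reading exercise with a little counting.

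**Step 1. Set the time limits side by side.** All are from the adverse-event section.

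| Who acts | What starts the clock | Limit |
|---|---|---|
| Principal Investigator is notified | Staff observe or hear of any possible event, by any route | 24 hours |
| Research meeting reviews events | Weekly routine | Weekly; the psychiatrist's attendance is not stated |
| Addiction Psychiatrist discusses a Moderate event | Study appointment | 7 days |
| Addiction Psychiatrist discusses a Severe event | Study appointment | 7 days |
| Addiction Psychiatrist discusses either grade, learned outside an appointment | Not stated | Not stated |
| IRB report, if the event meets all three listed criteria | Discovery | 1 week if serious, 2 weeks if not |
| Report of a death within 30 days of the intervention | Discovery | 24 hours |

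**Step 2. Look for another rule that brings the psychiatrist in sooner.**

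- The Principal Investigator's 24-hour notice carries no duty to pass a severe event on to the psychiatrist.
- Under Emergency care, participants are told to use emergency services, and the step for serious depression goes to the Principal Investigator.
- Section 4.4 says that the psychiatrist "will be available to provide patients with information regarding their side effects". That answers patients' questions; it does not set a review of an event.
- Section 3.4.2 excludes recent cardiac disease and sends anyone with a positive answer on the patch contraindications form to the psychiatrist. That happens at entry, before any on-study event.

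None of these sets an earlier deadline for the monitor.

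**Step 3. Count the ceiling.** Event learned at an appointment: 7 days × 1 patch a day = 7 patches before the discussion is required. Event learned by another route: no ceiling is stated.

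**Step 4. Find where the second gap matters.** During counseling, Section 4.2 schedules patch side effects weekly, so an event reported by telephone would probably come up again at the next session. After session 8 that support ends. Patches last 10 weeks from the Quit Date and counseling lasts 8 weeks, so at least 10 − 8 = 2 patch weeks follow counseling, assuming that the Quit Date is not before counseling starts. The plan does not give the Quit Date a session number. Section 3 has a follow-up after session 3 and the Section 4.2 table has a Quit Date column. If these are the same point, session 8 falls 8 − 3 = 5 weeks after quitting and 10 − 5 = 5 patch weeks remain.

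The Section 4.2 table and the payment schedule (Section 5.2, Subject Costs and Compensation) list no visit between session 8 and 3 months after the quit date. Section 3 mentions a one-month post-quit assessment that neither of them lists. With a Quit Date at session 3, it would fall at about the end of counseling and would not cover these weeks.

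**Step 5. Compare a tighter rule, measured to the same step.** Suppose the psychiatrist's discussion and decision are due by the end of the next business day after staff learn of the event. The longest ordinary case is Friday to Monday: 3 days × 1 = 3 patches. With a Monday holiday it is Friday to Tuesday: 4 days × 1 = 4 patches. The same ceiling would apply to unscheduled contacts.

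**The case against.** The strongest reply is that the plan's authors considered this. They state that their level of monitoring fits the degree of risk, and the product is an approved, over-the-counter patch used according to its insert. Cardiac risk and contraindications are screened at entry. The Principal Investigator hears of every event within a day, and events are reviewed every week. Seven days is a maximum, and the psychiatrist's monitoring role in Section 4.1.1 is not confined to appointments. The tighter limits proposed here are a reviewer's suggestion, not a requirement found in the documents.

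Much of this stands, and it keeps the point minor. It does not remove it. The general statement about risk gives no reason why Severe should have the same limit as Moderate, and a general monitoring role sets no time.

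Three stronger readings are tempting but unsupported:

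- A reader might infer that an event learned outside a visit has no time limit at all. It has: the notice to the Principal Investigator and the weekly review apply by any route, and the duty to discuss covers any logged item above mild. Only the deadline for the psychiatrist discussion is missing.
- A reader might take 7 patches as a measure of harm. It is a worst case. It supposes that the participant keeps applying patches and that nobody else intervenes, and the log is not limited to patch effects.
- A reader might treat Severe as meaning serious or urgent and see a conflict with the IRB timelines. Severe is a grade of intensity. The IRB limits govern reporting, and the documents show no conflict.

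**Conclusion.** The point holds as a minor patient-safety weakness. Followed exactly, the protocol allows 7 days from an appointment before a Severe event must be discussed with the medical monitor, the same as for Moderate. It states no deadline for that discussion when the event is learned another way. The ceiling is 7 daily patches in the first case and unstated in the second, which matters mainly in the patch weeks after session 8 (at least 2, or about 5 if the Quit Date is at session 3). A long delay is unlikely.

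The conclusion rests on the text available. The protocol refers to operating procedures set at the study team's initial meeting, which are not in the documents and may hold a faster route; the adverse-event section does not point to one. The consent pages are also unavailable, so what participants are told about stopping the patch cannot be judged.

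**What to change.** In the section on identifying, managing and reporting adverse events:

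- For any event graded Severe or possibly reportable to the IRB, notify the Addiction Psychiatrist within the same 24 hours as the Principal Investigator.
- Require the psychiatrist to document a continue-or-hold decision on the patch by about the end of the next business day.
- Keep 7 days for other Moderate events.
- Start both clocks when any staff member learns of the event, by any route.

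If the operating procedures already set such a route, cite it in this section instead.

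The cost is a short amendment and one more recipient on an existing notice in a 26-person study. The downside is a few extra calls to an existing co-investigator, some for events that prove minor or unrelated to the patch. No new staff or visits are needed.

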***Emergency care:***

Participants will be instructed to call 911 if they experience a medical emergency and Acute Psychiatric Services (APS) at [contact] if they experience a psychiatric emergency. The research assistant will administer a depression measure at the beginning of each session. If there is an indication that the patient is experiencing serious depression, the therapist will inform the patient and communicate concerns with the PI. The patient will be counseled accordingly and provided with appropriate emergency contact information.

***4.5 Potential for Benefit***

The benefits of taking part in this study include access to high-quality, smoking cessation treatment based on empirically supported psychosocial approaches. If participants quit smoking, they will experience health benefits; however, they may receive no direct benefit from taking part in this study.

***5. Subject Recruitment and Enrollment Considerations***

***5.1 Subject Recruitment***

The project will take place at our Rutgers offices in New Brunswick, NJ, located in the building next to a large University Behavioral Health Care outpatient clinic that serves more than 500 clients with a diagnosis of schizophrenia or schizoaffective disorder annually. We will recruit smokers from Rutgers University Behavioral Health Care, from private psychiatric intensive outpatient treatment providers, from the community via our website and local flyers, and via Rutgers listservs. Potential participants will call our offices for a telephone pre-screen. If potentially eligible, they will be offered a more in-depth in-person screening after providing informed consent. If all inclusion criteria are met, they will be invited to participate. This is an urban area with a large low-income population and therefore a greater proportion of smokers than the average of 14.8% in the state of New Jersey. Previous studies have given us the necessary experience with Rutgers listservs, websites, Craigslist, and use of flyers and brochures to maximize recruitment.

***5.2 Consent Procedures***

Participants will read a consent form or will have the consent form read to them before signing it. A trained research assistant (who will receive weekly and as-needed supervision from the principal investigator) will pre-screen potential participants on the phone, followed by obtaining informed consent and administering the baseline assessment battery. Trained research staff will proactively ask participants to describe the research study to them in their own words to ensure that participants understand the consent form. If there is any doubt of competence to consent, the individual will not be enrolled.

### ***5.2 Subject Costs and Compensation***

Participants will be paid \$100 through the duration of the study. They will receive \$40 at the baseline assessment (\$10 for first baseline session, \$30 for second baseline session), \$10 at the Quit Date assessment, \$30 at session 8, and \$20 at the 3-months post-quit date assessment.

## **6. Data Handling**

As this study is primarily a feasibility study, our data analysis plan will primarily comprise descriptive statistics such as mean (sd) sessions attended and percent of participants reporting 3-months post quit-date abstinence. We need to collect all of this data in order to demonstrate that our PTSC treatment manual is generalizable to a population of smokers with schizophrenia. We need to examine changes in relevant variables such as self-reported cigarette and medication use, withdrawal, smoking urges, and mechanisms of change in order to evaluate the efficacy of our treatment.

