### **3. Research Design and Methods**

We will conduct an open trial (N=26) of our 8-session, weekly, individual treatment, (Persistence Targeted Smoking Cessation for Schizophrenia (PTSC-S)). The purpose of this open trial will be to “begin to demonstrate that the intervention alters the targeted mechanism (thus providing an initial proof of principle).” We will measure task persistence via behavioral and cognitive measures administered in counterbalanced order at baseline, after session 3, and at one- and three-months post-quit date. By assessing task persistence at multiple follow-up points, we will be able to examine how many sessions are required to produce an effect (i.e., effect of treatment “dose”).

A trained research assistant (who will receive weekly and as-needed supervision from the principal investigator) will pre-screen potential participants on the phone, followed by obtaining informed consent and administering the baseline assessment battery (see Assessment Measures table below). We will divide the baseline assessment battery into two sessions to minimize participant fatigue. Each baseline assessment session will last approximately 90 minutes. We will then provide free, weekly individual counseling sessions for 8 weeks and 10-weeks’ worth of the nicotine transdermal patch (an FDA-approved smoking cessation product available over the counter). All sessions will be audio recorded for treatment integrity and supervision.

Questionnaires that are commonly used in tobacco dependence treatment studies will be used in the current study. Women of childbearing age will take a pregnancy test to rule out pregnancy. Carbon monoxide (CO) levels (also commonly collected in tobacco dependence treatment studies) will be assessed with a carbon monoxide monitor and CO reading in parts per million (ppm) will be recorded. The carbon monoxide monitor used will be the *Bedfont Scientific Ltd. Micro+ Smokerlyzer*. The Micro+ Smokerlyzer is a hand-held, battery powered instrument which uses electrochemical technology to sample the gas and a microprocessor to convert the output from the sensor to a carbon monoxide (CO) concentration. The result and menus are displayed on a color LCD and an accompanying buzzer sounds in response to the CO level. The instrument is controlled using a touch screen operation and has a USB link to a computer to download readings.

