The Micro+ uses a breath sampling D-Piece with integrated bacterial and viral filter and a one-way valve designed to maximize infection control. Each patient uses a fresh mouthpiece for each breath sample. The D-Piece may be reused or replaced as required.

The patient is asked to hold their breath for a 15 second countdown. This is displayed on the screen of the device. At the end of the breath hold, the patient blows gently into the Micro+ expiring as much of the breath in their lungs as possible. The reading on the device shall rise until the peak reading is held on the display.

A research assistant will provide instructions on how to use the CO monitor and will record the results at baseline and followup appointments. A research therapist will do so during the 8 counseling sessions. The study PI is accountable for the device.

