### **3.3 Sample Size Justification**

26 participants will be enrolled.

We will enroll 26 smokers from the local area. We will collect demographic data that will allow us to compare this sample to the general population of smokers. This is a non-randomized, pilot, feasibility study so a power analysis is not applicable to this study design.

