### **3.4 Subject Selection**

#### **3.4.1 Inclusion Criteria**

- Must be between 18 – 64 years old
- Must indicate commitment to quitting smoking in the next 30 days
- Must smoke at least 5 cigarettes (including those labeled “little cigars”) per day for past 6-months
- Expired breath carbon monoxide (CO) > 5 to ensure daily cigarette use
- Must score < 8 (or <7 for women) on the Alcohol Use Disorders Identification Test
- Must score less than 3 on the 6-month Drug Abuse Screening Test-10
- Must provide a negative urine drug screen for cannabis, cocaine, or opiates (Note: Participants with a positive screen for opiates may participate with proof of prescription for opiates.)
- Must have a diagnosis of Schizophrenia or Schizoaffective Disorder on SCID-I
- Psychiatric illness must be stable, as indicated by no hospitalizations in previous 8 weeks, and a stable psychotropic medication regimen including a stable antipsychotic dose for 8 weeks
- Must have a working phone (for feasibility of follow-up and for ability to receive optional SMS text messages)

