#### 4.2 Dependent Variables or Outcome Measures

Assessment measures: See table below

Concept	Measure	B/L	Weekly	QD	Session 8	3-mo. Post QD
DEMOGRAPHICS	Smoking History & Demographics Questionnaire (includes National Health and Nutrition Examination Survey (NHANES) items)	X				
TOBACCO USE	Fagerström Test for Nicotine Dependence (Heatherton et al., 1991)	X				
	Timeline Followback (TLFB; Sobell & Sobell, 2000)		X	X	X	X
	Current Tobacco Use – \$ spent, menthol use, night-time smoking	X				
	Expired Breath Carbon Monoxide (CO)	X	X	X	X	X
	Brief WISDM	X				
NRT USE	Self-reported use of patch – including visual inspection of patch		X	X	X	X
	NRT side effects		X	X	X	X
	Nicotine patch contraindications form	X				
CRAVING AND WITHDRAWAL	Wisconsin Smoking Withdrawal Scale (Welsch et al., 1999)	X	X*	X	X	
MOTIVATION TO QUIT SMOKING	ICT – Change Measure (includes self-efficacy) (Miller & Johnson, 2008)	X		X	X	
	Quitting Fatigue			X	X	X
	Commitment to Quitting Smoking Scale (CQSS)	X		X	X	
ANHEDONIA	Temporal Experience of Pleasure Scale (Gard et al., 2006)	X		X	X	X
	Snaith - Hamilton Pleasure Scale (Snaith et al., 1995)	X		X	X	X
	Tripartite Pleasure Inventory (Leventhal, 2010)	X		X	X	X
TASK PERSISTENCE	Mirror Tracing	X		X	X	X
	Breath-holding	X		X	X	X
	Temperament and Character Inventory—Persistence Scale (TCI-P)	X		X	X	X
	2-item Task Persistence Measure	X		X	X	X
	Distress Tolerance Scale (DTS)	X		X	X	X
	Sustained Divided Attention Task	X		X	X	X
	Thoughts About Smoking Questionnaire	X		X	X	X
	Daily Habits Questionnaire	X				
SUBSTANCE USE / MENTAL HEALTH ISSUES	Alcohol Use Disorders Identification Test (AUDIT; Babor et al., 2001)	X				
	6-month Drug Abuse Screening Test – 10 (DAST-10; Skinner, 1982)	X				
	Urine drug screen (for cannabis, cocaine, opiates)	X				
	SCID-RV for DSM 5 - Modules A, B, and C	X				
	Brief Symptom Inventory (BSI; (Derogatis, 1975)	X				
	CES-D	X	X	X	X	X
INTERVENTION INTEGRITY / FEASIBILITY	Exit interview		X	X	X	
	Study created integrity measure		We will confirm treatment integrity throughout the study			

\*Wisconsin Smoking Withdrawal Scale will be administered before sessions 4 through 8

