### ***Data collection:***

The majority of data will be collected through face-to-face interview. A research assistant will read the questions to the participants while they read along from their own copies of the measures to maximize participant comprehension. If participants are unable or unwilling to attend a follow-up appointment at our Rutgers RWJMS offices, a research assistant will meet the participant off-site, in a public location agreeable to the participant such as a local public library. If off-site appointments are also impossible, we will conduct telephone interviews. Data will be stored at the Division of Addiction Psychiatry; [name]. Only the IRB-approved research team will have access to the research data.

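### The 3-month quit rate in Section 6 is worded as self-report, and the expired CO already scheduled at that assessment is not used to confirm it (minor)

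*Combined protocol and SAP*

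**What the plan says.** Section 6 describes a mainly descriptive analysis and gives two examples: sessions attended and the "percent of participants reporting 3-months post quit-date abstinence". The same section calls the cigarette-use data self-reported and does not mention CO.

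The schedule in Section 4.2 has a row beginning "Expired Breath Carbon Monoxide (CO", placed under tobacco use and marked at every column, including 3 months post quit date. The TLFB is marked at that assessment too. Section 3 says that readings are recorded in ppm and that a research assistant "will record the results at baseline and followup appointments".

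The only CO threshold is the entry criterion in Section 3.4.1: "Expired breath carbon monoxide (CO) > 5 to ensure daily cigarette use". It stands beside a criterion on the number of cigarettes smoked per day.

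Under Data collection in Section 6, a participant who does not come to the office is seen elsewhere ("a research assistant will meet the participant off-site"). The last step is: "If off-site appointments are also impossible, we will conduct telephone interviews".

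Section 8.2 lists the proportion of participants who obtain abstinence among the aggregate results that may be presented, published or put in grant applications. It does not define abstinence. Section 7 mentions neither abstinence nor CO.

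**The concern.** The statistic that Section 6 names counts participants who say they have stopped smoking. The statistic that Section 8.2 expects to report concerns participants who have stopped. The two agree only if every report is accurate, and the plan has no step that checks this, although it collects a reading that could.

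The plan applies such a check elsewhere. At entry, CO serves as objective support for daily smoking. At 3 months the same instrument is used, but the plan stops at recording the value. The TLFB does not fill the gap: it is also self-report, so it can define the period of abstinence but cannot verify it.

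What is at stake is the meaning of one descriptive percentage that may be carried into publications and grant applications. The cut-off, the window and the handling of missing readings are all unset. Section 7 says that data are reviewed every quarter, so these choices could be made after results have been seen.

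**Working it through.** The plan states no expected quit rate, misreporting rate or precision for abstinence, so there is no figure of its own to reproduce. The check is a comparison of the text, followed by a calculation of scale.

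**1. Text comparison**

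| Place | What it gives | What it does not give |
|---|---|---|
| Section 6 | Quit rate, worded as reported | Window, CO criterion, denominator |
| Section 4.2 | CO and TLFB at 3 months post quit date | A link from either to abstinence |
| Section 3 | CO recorded in ppm at follow-up | A use for the recorded value |
| Section 3.4.1 | CO above 5 for entry | An abstinence cut-off |
| Section 6, Data collection | Telephone as last fallback | Status of a case with no breath sample |
| Section 7 | Tests for hypotheses 1 and 2 | Any mention of abstinence or CO |
| Section 8.2 | Proportion obtaining abstinence may be reported | A definition |

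A confirmed rate cannot be derived from these sections, because no cut-off or rule is stated.

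**2. Size of one unconfirmed report**

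Input: N = 26, from Section 3.3 ("26 participants will be enrolled"). If k participants report abstinence and u of those reports are not confirmed, the reported rate is k/26 and the confirmed rate is (k − u)/26. The difference is u/26, so one unconfirmed report moves the rate by 1/26 = 3.8 percentage points and two move it by 2/26 = 7.7 points, whatever k is.

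**3. Illustration over assumed values**

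Neither k nor u is in the documents. The values below are assumptions for scale only.

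| Assumed k | u = 0 | u = 1 | u = 2 |
|---|---|---|---|
| 5 | 5/26 = 19.2% | 4/26 = 15.4% | 3/26 = 11.5% |
| 7 | 7/26 = 26.9% | 6/26 = 23.1% | 5/26 = 19.2% |
| 10 | 10/26 = 38.5% | 9/26 = 34.6% | 8/26 = 30.8% |

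**4. Scale against sampling uncertainty**

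The exact (Clopper-Pearson) 95% limits for x of n are the 0.025 quantile of Beta(x, n − x + 1) and the 0.975 quantile of Beta(x + 1, n − x). With n = 26:

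- 7/26: 11.6 to 47.8%, width 36.2 points
- 6/26: 9.0 to 43.6%, width about 35 points
- 5/26: 6.6 to 39.4%, width 32.8 points

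A shift of 3.8 or 7.7 points is small beside these widths. The plan specifies no interval for abstinence; these are shown only for comparison.

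**5. Direction**

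Requiring both a report and a CO value can only leave the rate unchanged or lower it. That follows from the definition and is not evidence that misreporting will occur.

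**The case against.** The strongest reply is that the plan is silent rather than wrong. The Section 6 list is illustrative. CO is a declared outcome measure at the 3-month assessment, and Section 8.2 uses wording that does not depend on report. The team could compute a confirmed rate at write-up from data it will hold. Abstinence is in neither hypothesis in Section 1.2, there is no comparison arm, and the limitations paragraph already asks for caution.

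Most of this stands, and it is why the point is minor. A reader might infer that the sponsor has decided to publish a self-reported rate only; the documents do not say so and do not rule out a confirmed rate. What remains is that the one quit-rate statistic named is worded as report, and no rule connects it to the CO reading.

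A second reply is that a single CO reading cannot verify a long window, that the documents offer no abstinence cut-off, and that counting missing readings as unconfirmed can lower the rate through non-attendance rather than smoking. These are fair limits. They call for a short window, parameters fixed in advance, and both rates reported; they do not support leaving the reading unused.

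**Conclusion.** The point holds as a minor gap in an outcome definition. Each unconfirmed report lowers the rate by 3.8 percentage points, taking all 26 enrolled as the denominator. The number of such reports is unknown and may be zero. Neither hypothesis depends on the result.

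Three stronger readings are tempting and are not supported:

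- A reader might infer that the reported quit rate will be inflated by some known amount. The documents contain no information on misreporting.
- A reader might infer that few participants will lack a CO reading, because the monitor is a "hand-held, battery powered instrument which uses electrochemical technology" and telephone is the last resort. The documents do not say that the monitor goes to off-site meetings, and they give no rate of telephone contact or loss to follow-up.
- A reader might fault the confidence interval for the self-reported rate for ignoring the downward shift. The plan specifies no such interval, so there is nothing to fault.

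**What to change.** Add two or three sentences to Section 6:

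- Report CO-confirmed point abstinence at 3 months post quit date, defined as no smoking on the TLFB over a short window **and** expired CO at that visit at or below a cut-off. Fix the window and the cut-off before any data review.
- The cut-off could, for example, be set so as not to exceed the protocol's own entry value of 5. The documents do not present that value as an abstinence rule, so the choice needs its own justification.
- State that a single CO reading may support only part of the TLFB window.
- Use all 26 enrolled as the denominator and count cases without a CO reading as not confirmed.
- Report the self-reported rate and the number without a CO reading alongside.

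This is cheap: CO and TLFB are already scheduled at 3 months, so no new measurement or visit is needed. The downside is that the confirmed rate may be lower, and true quitters reached only by telephone would count as unconfirmed. How many that would be is unknown from the documents; showing both rates makes the effect visible.
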